RE: "Changes in Vertebral Artery and Cerebral Hemodynamics Following Various Head Positions & Cervical Manipulation in Patients with Chronic/Recurrent Neck Pain."

Co-Investigators:

[name], BSc DC

[name], DC PhD

[name], DC PhD

[name], DC PhD

[name]

[name]

To whom it may concern,

We thank you for your consideration of this work. Please find below 4 pages detailing the methods and procedures of the study.

Sincerely,

[name], BSc, DC

Methods

Participants

Twenty patients were recruited from the campus-teaching clinic located at the Canadian Memorial Chiropractic College. Included were adults aged 18 years and older with chronic grade II/III mechanical neck pain that had been prescribed cervical manipulation for treatment of their condition. Patients with a history of neck pain with associated arm pain within the last 6 months; any current or history of neurologic symptoms including facial or extremity weakness, abnormal sensation to the face, body, or extremities, uncontrolled movements, abnormal gait, dizziness, unexplained nausea/vomiting, difficulty with speaking or swallowing; history of new or severe (Visual Analogue Scale >6) headaches in the last 3 months; any contraindications to MRI; or any history of using drugs that affect blood flow such as Warfarin, or anti-coagulants were excluded. All participants refrained from vigorous physical activity, alcohol, and caffeine one day before commencement of the study.

The study was approved by the local ethics committees of St. Joseph's Healthcare Hamilton at McMaster University in Hamilton, Ontario, and Canadian Memorial Chiropractic College in Toronto, Ontario. Written informed consent was obtained from all participants before the study commenced. Data were collected at the Imaging Research Centre, Hamilton, Ontario. The study was registered with www.clinicaltrials.gov, NCT02667821.

Test Protocols

The study was conducted as a randomized controlled case-crossover trial. Prior to the MRI, baseline information on each participant was obtained and included age, gender, height, weight, hand dominance, NDI score neck pain intensity and headache intensity (see Table 1). On the day of the scan, prior to commencing, participants underwent a cervical spine examination, completed by the clinician performing the test maneuvers (SM), in order to identify the site of manipulation. Once participants provided verbal acknowledgement of being comfortable to proceed, they underwent three separate test maneuvers. Each began with neutral (0 degree rotation) neck position (condition 1) as a standard natural control, followed by either maximum voluntary rotation (conditions 2), and one dynamic high-velocity-low-amplitude (HVLA) cervical rotary manipulation targeted at C1-C2 (condition 3). Each procedure was performed to the side of clinical findings elicited during cervical examination by the clinician. Tasks were selected based on their use in evaluation or treatment during clinical encounters.

Neutral position of the head was defined by alignment in the Frankfort plane in a vertical orientation. For continuity of neutral alignment between protocols, the MRI laser land marking tool was used to cross triangulate three tape marks on the MRI head RF coil with three oil based markers (Vitamin E capsules) taped to the nasion (bridge of the nose) and immediately in front of the tragus of the ears, bilaterally. For each brain image obtained, the marker set provided quantitative orientation of the head position.

Participants were randomly assigned to condition 2 or condition 3 using a randomized table generator (GraphPad Software Inc, La Jolla, CA). Each head condition was applied in the MRI scanner room adjacent to the MRI bore (Fig 1) and for condition 2 the position of the head was held for 1 minute and then returned to neutral for MRI sequencing. For the manipulation, the head was repositioned to neutral immediately after

and the patient was retracted into the MRI bore. Condition 2 was independently measured by inclinometer.

After each condition, MRI of the cerebrum and upper neck for blood flow ensued. The total time elapsed for each participant testing protocol was 60 minutes. The total time elapsed for each condition was approximately 20 minutes. This included applying the condition (1 minute), replacing the participant back into the MRI bore (approximately 1 minute), and routine image sequencing (approximately 18 minutes). Estimates of repeatability of flow measures were made in preliminary work by quantifying VA flow in a single healthy participant twice over a 2-month interval.

A practitioner with more than 30 years of practice experience conducted the upper cervical manipulation.³²⁻³⁴ The manipulation procedure required no transfer of the participant; rather, it was performed on the adjustable and pivotal MRI bed in the MRI room with the participant in the supine position (Fig 1). The procedure was a high velocity, low amplitude (HVLA) impulse, designed to initially position the participants' heads in an axial rotation, flexion as well as lateral flexion postures. Variations of head positions between operators have been demonstrated to be relatively small.^{35,36} The clinician performed the procedures in representative manner, first establishing the end range of motion to determine appropriate preload position for the manipulation before applying a typical clinical force impulse in the coronal plane with minimal traction component. Before the delivery of each maneuver, the participants were queried on their comfort, condition, and willingness to continue.

A brief 5-item analogue scale was administered to each of the participants and clinician immediately after the test maneuvers. This scale provides quantitative estimates of the patient's and operator's judgment of the descriptive characteristics of the CSM procedure on a continuous scale of 0 to 10. The words "fast," "force," "comfort," "confidence," and "precise" were used as descriptors as validated and used in several other studies.³⁷⁻³⁹ The scale provided a means of contrasting the procedure characteristics within the context of the range of typical performance, as represented within the literature.

Magnetic Resonance Imaging Protocols

Four MRI series were performed on each participant (3-Telsa GE Signa Excite HD MRI scanner and 20 channel neurovascular array RF coil; GE Healthcare, Milwaukee WI), including anatomical images, arterial spin labeling (ASL), blood oxygen level dependent (rsMRI BOLD) and phase contrast MRI. Following head positioning, immobilization with sponges and a localizer scan, anatomical images were collected using a 3D IR-prepped fast SPGR T1-weighted scan (TR/TE=11.4/4.3 ms, T1 = 450 ms, flip angle = 12 degrees, 512 x 256 matrix, 140 slices, 24 cm FOV, reconstructed to 1mm³ isotropic voxels). Microvasculature was assessed using a 3D spiral-based fast spin echo pseudo-continuous arterial spin labeling (pCASL). pCASL sequence was used to assess cerebrovascular perfusion (TE/TR/TI=10.5/4629/1525ms, FOV=24cm, 512x8spiral interleaves, 3NEX, reconstructed to 128x128matrix with 4mm thick slices, scan time =30s). The ASL sequence was immediately followed with the phase contrast MRI. At the level of C1-2, the contralateral and ipsilateral vertebral arteries (to the direction of head motion) were assessed and anatomical images were established to localize the VA circulation. As previously published by Ho et al the method for obtaining flow quantification of the VA was a 2-dimensional phase-contrast pulse sequence. To capture accurate VA flow, the imaging plane is ideally perpendicular to the central axis of the

blood vessel. This imaging plane was selected on the vessel of interest at the C1-2 intervertebral level based on arterial visualization on a maximum intensity projection of a 2-dimensional time-of flight MRI angiogram. Magnetic resonance acquisition parameters were as follows: fast gradient recalled echo; echo time/repeat time, 3.9/8.9 milliseconds; flip angle, 20°; 20 cm field of view; 512* 512 matrix; 244-Hz/pixel receiver bandwidth; 1 average; 4 mm thick; and velocity encoding of 50 cm/s encoded for 30 phases per cardiac cycle. Owing to anatomical variations, occasional slices could only approximate orthogonality. All image measurements were obtained by manually selecting the optimal anatomical site between the base of the odontoid process and approximately 1 cm above the tip of the dens. According to Lotz et al vessel obliquity is tolerable to above or equal to 15 degrees, above which will cause a deviation from the true flow.⁴¹ Data capture was triggered by prospective gating using a peripheral pulse (MRI scanner-pulsed oximeter). The image acquisition time for each flow measurement was approximately 1 minute 30 seconds depending on heart rate. Flow analysis was performed using Segment v1.9 software⁴⁷ (Medviso, Lund, Sweden). Dynamic regions of interest were drawn on the left and right vertebral arteries to quantify mean, as well as peak velocities, and flows. Data in the trigger window portion of the cardiac cycle were derived by spline interpolation using Matlab (Mathworks, Natick, MA). The final data set for a complete cardiac cycle, therefore, contained measurements from all the cardiac cycles that elapsed during the scan time. A typical phase-contrast image is presented in Figure 2, with regions of interest (ie, vascular cross sections) labeled. Subsequently, rsMRI BOLD was performed. This was acquired using a gradient echo, echo planar imaging (GE-EPI) sequence (64x64 matrix, 28 axial slices (5mm thick, no skip), 24cm FOV, TE/TR/flip angle = 35ms/2000ms/90°, 180 temporal points, total scan time=6 minutes). During the rsMRI BOLD scan, subjects were asked to keep their eyes open, stay awake, and not think of anything in particular.

Following the 3D anatomical, rsMRI BOLD, ASL and phase contrast MRI the subject was removed from the MRI and condition 2 and 3 were applied separately in a randomized order. Each condition was immediately followed by realignment of the head, return to the MRI bore, scan of a 3-plane localizer and then ASL, phase contrast, rsMRI BOLD and 3D anatomical scans. The latter three were always performed with the 3D anatomical last seeing as microvascular changes (i.e. blood flow) were more likely to be detected early after the manipulation while structural changes (i.e. 3D scan) wouldn't be expected to occur.

Data Analysis

Data quantification was performed by an experienced analyst who remained blinded to the test maneuvers. ASL blood flow and rsMRI BOLD data were analyzed using analysis of functional neuroimaging (AFNI). Functional rsMRI BOLD data preparation first involved slice timing correction and 3D rigid body motion correction. For each subject all ASL and rsMRI BOLD data were spatially registered to the initial (neutral condition) position. Anatomical, blood flow and functional data were transformed automatically to the Colin27 atlas, using the AFNI command @auto_tlrc, with functional data resampled to a 2mm isometric grid.⁴² Temporal band-pass filtering with cutoffs of $0.009\text{Hz} < f < 0.08\text{Hz}$ was performed in order to suppress unwanted physiological signals and some hardware noise.⁴³ Functional connectivity within the default mode network (DMN) was assessed using the AFNI plugin InstaCorr, a seed-based approach, which uses the Pearson

method of correlation to compare time signals.⁴⁴ The DMN is the most dominant temporally correlated resting network in the awake brain, defined as regions positively correlated in time with the posterior cingulate cortex (PCC) seed voxel. The PCC was defined automatically using the AFNI Talairach method ‘Talairach to’ and selecting a single voxel from each the left and right PCC for one analysis (ColinN27 coordinates: 10, 54, 14, and -10, 54, 14). These were both subsequently fused in the post-processing. A 5mm FWHM Gaussian spatial smoothing filter was applied for maximize likelihood of overlap with inter-subject group analysis. Also, temporal outliers determined with the AFNI function 3dToutcount were censored out. The ASL cerebral blood flow data was analyzed similar to rsMRI BOLD in that following spatial co-registration to the neutral condition and spatial blurring with a 5mm FWHM Gaussian convolution kernel, ASL data was warped to the N27 atlas. Group analysis was accomplished using a 1-way within subject 3D-ANOVA, with the one factor being neck position. Post hoc testing included contrasts between neutral, maximum voluntary rotation and CSM, and also a contrast between maximum voluntary rotation and CSM. Statistical significance was defined as anything lower than an alpha value of 0.05.

Mean and SDs were calculated for VA blood velocity, flow, peak velocity, and peak flow for each of the head conditions and VA side. Differences between task maneuvers and VA flow and velocity were evaluated using a repeated-measures analysis of variance with factors of head position and VA side, and a level of significance was set at .05, using R-project version 2.12.1 (R Development Core Team, 2010. R: A language and environment for statistical computing. R Foundation for Statistical Computing, Vienna, Austria. ISBN 3-900051-07-0, URL <http://www.R-project.org/>).

Ratings for the perception of performance of the HVLA cervical manipulation procedure were expressed quantitatively as the distance along the VAS line of intensity for each descriptive term as a percent of the total length. In this form, the results were expected to represent the typical experience at midpoint (e.g. 5 of 10). A composite rating was developed as the average across all descriptive terms, assuming equal weighting, as an index of the overall experience. As secondary variables, descriptive statistics were calculated and Student-tests were performed between the raters using Bonferroni correction for significance of p less than or equal to 0.01. ICCs were also calculated examining for correspondence between raters.

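### Main-effect comparisons with neutral are confounded with period and series order, and the randomised manipulation-versus-rotation contrast is not named for vertebral artery flow

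*Combined protocol and SAP*

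**What the plan says.** All places are in the Combined protocol and SAP.

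- **Condition order.** Test Protocols: "Each began with neutral (0 degree rotation) neck position (condition 1) as a standard natural control". Randomisation concerns only the other two conditions: "Participants were randomly assigned to condition 2 or condition 3 using a randomized table generator". The last paragraph of Magnetic Resonance Imaging Protocols makes clear that each participant receives both, after the neutral scans: "condition 2 and 3 were applied separately in a randomized order".
- **Series order at neutral.** That paragraph lists the neutral series as "Following the 3D anatomical, rsMRI BOLD, ASL and phase contrast MRI the subject was removed from the MRI". The general description earlier in the section also starts with the anatomical scan ("Following head positioning, immobilization with sponges and a localizer scan, anatomical images were collected"), then gives ASL and phase contrast ("The ASL sequence was immediately followed with the phase contrast MRI"), and then BOLD ("Subsequently, rsMRI BOLD was performed"). The two texts place BOLD differently, but both put the anatomical scan first.
- **Series order after each manoeuvre.** "scan of a 3-plane localizer and then ASL, phase contrast, rsMRI BOLD and 3D anatomical scans". The anatomical scan is always last here, and a reason is given: flow changes were expected early after the manipulation and structural change was not expected.
- **Analysis.** Data Analysis gives ASL a one-way within-subject ANOVA on neck position, with post hoc contrasts against neutral and between rotation and manipulation. For VA flow and velocity it gives a repeated-measures ANOVA with head position and VA side, and names no contrast. Neither model has a period or sequence term.

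**The concern.** Neutral differs from the two manoeuvre conditions in three ways at once: the manoeuvre itself, the place in the session, and the series order. ASL and phase contrast at neutral are acquired later after positioning, because the anatomical scan comes before them, yet earlier in the session. The plan's own reason for the post-manoeuvre order implies that timing after positioning matters for flow, but it does not acknowledge that neutral is timed differently.

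A difference from neutral in ASL, or a significant three-level VA head-position test, could therefore arise with no manoeuvre effect. The comparison that randomisation protects is manipulation against rotation. For VA flow it is left inside a 2-df test that mixes it with the confounded neutral comparison.

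**Working it through.** **1. How many neutral scans?** Test Protocols gives 1 min for the condition + 1 min to return to the bore + 18 min of imaging = 20 min per condition, and 60 min in total. 3 × 20 = 60, as stated. A second neutral block would need 80 min. So there is one neutral block, and it is first.

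**2. What can be estimated?** The possible orders are neutral–rotation–manipulation (order A) and neutral–manipulation–rotation (order B). Take columns for intercept, rotation, manipulation, period 2 and period 3. In every row, rotation + manipulation = period 2 + period 3, so the rank is 4 of 5. Manipulation − rotation is estimable; rotation − neutral and manipulation − neutral are not. An anatomical-first column equals intercept − rotation − manipulation, so adding it leaves the rank at 4. This needs no assumption about drift.

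**3. Timing.** The anatomical scan time is not stated. Assumptions:
- Unaccelerated, inversion delay ignored: 0.0114 s × 256 × 140 = 408.6 s = 6.8 min.
- Two-fold acceleration: 3.4 min.
- Upper end from the 18-min block: 18 − 6 (BOLD) − 0.5 (ASL) − 1.5 (one flow scan) − 2 (localizer and angiogram, assumed) = 8.0 min. With two flow scans it is 6.5 min.

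So neutral ASL is about 3.4 to 8 min later after positioning than post-manoeuvre ASL. On the session clock, post-manoeuvre imaging starts at 20 + 2 = 22 and 40 + 2 = 42 min. If neutral imaging starts at 0 to 2 min and BOLD follows phase contrast, neutral ASL falls at 3.4 to 10 min. It is then earlier by 12 to 18.6 min and by 32 to 38.6 min. If the neutral list is chronological, BOLD adds 6 min: 9.4 to 16 min, with gaps of 6 to 12.6 and 26 to 32.6 min.

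**4. What drift could do (drift sizes assumed).** Suppose no manoeuvre effect and a step of d residual SDs after the first block, with n = 20. The three-level test at 0.05 is noncentral F(2, 38) with noncentrality 20 × (2/3)d². It rejects 11%, 33%, 65% and 89% of the time at d = 0.25, 0.5, 0.75 and 1.0; a simulation at d = 0.5 gave 33%.

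**5. The randomised contrast.** Let M and R be the condition effects, p the second-to-third period shift, and cM and cR the carryover of manipulation and rotation into the third block. Each participant's manipulation-minus-rotation difference has expectation:
- order A: (M − R) + p + cR
- order B: (M − R) − p − cM

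Unadjusted, a 13:7 split absorbs (13 − 7)/20 = 30% of p; 12:8 absorbs 20%; 10:10 none. If the 20 participants were allocated without balancing (not stated), P(10:10) = 0.176 and P(13:7 or more unequal) = 0.263.

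With sequence coded +1/−1 and not centred, the intercept is the mean of the two lines: (M − R) + (cR − cM)/2. Period is removed; half the carryover difference stays. With M − R = 1, cM = 1 (full persistence, assumed) and cR = 0, it returns 0.50.

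The neutral-to-second-block change, order B minus order A, returns M − R, here 1.00. First-period, series-order and carryover terms cancel.

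**6. Price of the period term.** Degrees of freedom go from 19 to 18 (critical t from 2.093 to 2.101). Variance inflation is 0.25(1/n₁ + 1/n₂)/(1/20) = 1.042 at 12:8 and 1.099 at 13:7.

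**The case against.** The strongest replies, and what stands of each:

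- **A first-scanned baseline is ordinary, and the post-manoeuvre order has a reason.** Both are true, and that order is the same for both randomised conditions. The reason does not cover the difference from neutral.
- **Not every use of neutral is compromised.** This stands. A reader might infer that nothing involving neutral can be interpreted. Yet a position-by-side interaction compares ipsilateral with contralateral arteries within a condition, so an additive shift common to both cancels. Side-specific or proportional shifts would remain, and Data Analysis does not name the interaction. The neutral-to-second-block change compared between orders also uses neutral validly.
- **Manipulation minus rotation is not the only route to a manipulation-specific claim, nor free of bias.** This stands. Conditions are about 20 min apart, and carryover enters as shown. The second-block comparison is robust to it but rests on about 10 against 10 participants.
- **Randomisation already deals with period.** It does so in expectation. The 30% figure needs both a chance 13:7 split and a real period shift. The period term is cheap protection, not the repair of a demonstrated error.
- **The timings are soft.** This stands. They rest on assumed scan parameters, and only the broad range should be quoted.
- **Adding VA contrasts multiplies tests.** This stands. Four measures on two sides are eight tests; at 0.05 each, the chance of a false positive is up to 1 − 0.95⁸ = 34% if they are independent.

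**Conclusion.** The point holds in limited form. The ASL contrasts with neutral and the three-level VA head-position test are fully confounded with period and series order; this follows from the design alone. For VA flow and velocity the randomised contrast is not named, and neither ANOVA has a period term.

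A reader might go further and infer that differences from neutral are artefacts, or that the trial is invalid. The documents support neither. They give no within-session drift: the only repeatability evidence is one healthy participant measured twice over 2 months. The rejection rates of 11% to 89% show what assumed drifts would do, not what happened. The randomised contrast survives, subject to carryover. Nor is the placing of BOLD at neutral a proven contradiction, since the later list may be an inventory; it changes the timing gap by 6 min and not the confounding. The change should be made, because it decides which comparison can carry a claim about manipulation.

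**What to change.** 1. **Name the contrast.** For VA flow and velocity, specify within-participant manipulation minus rotation by VA side, as is already done for ASL. Name one VA measure as the main one, or adjust across the eight tests. For VA and ASL, include the period term (regress each participant's difference on sequence coded +1/−1, uncentred, and read the intercept). Report the number in each order. If the data have already been analysed, label the VA contrast as added.
2. **Base manipulation-specific claims on it.** State that it is biased by half of (rotation carryover minus manipulation carryover). Report the neutral-to-second-block change, compared between the randomised orders, as a carryover-robust sensitivity analysis.
3. **Keep the comparisons with neutral**, described as change from a first-scanned baseline that is confounded with session time and series order.
4. **Reconcile the text.** Make Magnetic Resonance Imaging Protocols state one neutral series order, and align the assignment wording in Test Protocols with the randomised order described there. Report ASL and phase-contrast start times from the image headers for all three conditions, from positioning and from session start.

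Cost: no new scans. The period term takes 1 df and adds 4% (12:8) or 10% (13:7) to the variance. The voxelwise ASL model must be re-run, the sensitivity analysis is less precise, and the neutral comparisons carry a weaker claim.

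### Rotation and manipulation follow each other about 20 minutes apart with no neutral rescan between them, and the analysis has no order or period term, so carry-over could bias the randomised contrast unseen.

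*Combined protocol and SAP*

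**What the plan says.** The section Test Protocols describes the design: "The study was conducted as a randomized controlled case-crossover trial". On allocation it says: "Participants were randomly assigned to condition 2 or condition 3 using a randomized table generator". The section Magnetic Resonance Imaging Protocols makes clear that every participant receives both manoeuvres. A full neutral scan set comes first, then "condition 2 and 3 were applied separately in a randomized order". It continues: "Each condition was immediately followed by realignment of the head, return to the MRI bore". No rest period and no second neutral scan are described before the second manoeuvre.

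Test Protocols gives the timing: "The total time elapsed for each condition was approximately 20 minutes", and "The total time elapsed for each participant testing protocol was 60 minutes".

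One sentence in Test Protocols points another way. Of the three test manoeuvres it says: "Each began with neutral (0 degree rotation) neck position (condition 1) as a standard natural control". This could be read as a neutral control scan before each manoeuvre.

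Under Data Analysis, the imaging model is stated as: "Group analysis was accomplished using a 1-way within subject 3D-ANOVA, with the one factor being neck position". Vertebral artery (VA) flow and velocity are analysed by repeated-measures analysis of variance with head position and VA side as factors. Post hoc contrasts for the imaging data compare each manoeuvre with neutral and the two manoeuvres with each other. No results by order are planned.

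**The concern.** In a crossover, randomising the order balances drift over time between the two manoeuvres on average. It does not protect against an effect of the first manoeuvre that is still present when the second is measured. About half the participants have their rotation scan after a manipulation, and about half have their manipulation scan after a rotation.

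A lasting manipulation effect would be partly credited to rotation, and the reverse is also possible. The contrasts at stake are rotation versus manipulation, which is the only one supported by the randomised order, and whichever manoeuvre-versus-neutral contrast receives the carried-over effect. With order absent from both models and from the planned output, a reader could not tell a real absence of difference from contaminated scans.

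**Working it through.** **Timing, from Test Protocols.** Each condition takes 1 min (apply) + 1 min (return to the bore) + 18 min (imaging) = 20 min. Three conditions take 3 × 20 = 60 min, which reproduces the stated session length. The remainder is 60 − 60 = 0 min, so a neutral rescan before the second manoeuvre does not fit. The second manoeuvre starts about 20 min after the first, and its arterial spin labelling (ASL) scan starts at about 20 + 1 + 1 = 22 min.

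**Bias.** Let m and r be the true effects of manipulation and rotation against neutral. Let f be the fraction of an effect still present at the next block, with equal numbers in each order. The documents give no value for m, r or f and state no balancing of the orders; all are assumptions here.

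- Only manipulation carries over: mean rotation scan = r + fm/2, so observed manipulation − rotation = m − r − fm/2.
- Both carry over by the same fraction: observed contrast = (m − r)(1 − f/2).
- With r = 0, both give m(1 − f/2). Manipulation carry-over also gives rotation a false effect of fm/2 against neutral.

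If the effect decays exponentially (also an assumption), f = 2^(−20/half-life):

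| Half-life (min) | f | Contrast understated by f/2 |
|---|---|---|
| 3 | 0.01 | 0.5% |
| 5 | 0.06 | 3% |
| 10 | 0.25 | 12.5% |
| 20 | 0.50 | 25% |
| 60 | 0.79 | 40% |
| no decay | 1 | 50% |

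**Direction is not fixed.** With carry-over from manipulation only:

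- m = 1, r = 0.5, f = 1: true contrast 0.5, observed 1 − 0.5 − 0.5 = 0. The difference vanishes.
- m = 0.5, r = 1, f = 1: true contrast −0.5, observed 0.5 − 1 − 0.25 = −0.75. The difference widens.

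**Unequal orders.** If k of 20 have manipulation first and r = 0, the share of the contrast retained is 1 − fk/20. Simple randomisation gives k from 6 to 14 (95% range). At f = 1 that retains 70% to 30%.

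**Effect on the tests.** Simulation of 40,000 trials: n = 20, 10 per order, r = 0, m = 0.8 SD of the paired difference, scans equally correlated, two-sided 0.05.

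| f | False rotation-versus-neutral finding | Power, manipulation versus rotation | Power, manipulation versus neutral |
|---|---|---|---|
| 0 | 5% | 92% | 92% |
| 0.5 | 13% | about 70% | 92% |
| 1 | 34% | 34% | 92% |

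**Could a carry-over test detect it?** Compare the two orders on each person's mean post-neutral change. With unit SD of the paired difference, each scan has variance 0.5, so this change has variance 0.25 + 0.5 = 0.75. The SE of the difference between orders is √(0.75 × 2/10) = 0.387. The difference between orders is 0.8f/2, which is 0.2 at f = 0.5 and 0.4 at f = 1. Power is about 8% and 16%.

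**First-manoeuvre-only comparison.** With per-scan variance s², the paired contrast has variance 2s²/20 = 0.1s². Change from neutral compared between two groups of 10 has variance 2 × 2s²/10 = 0.4s². The SE ratio is √(0.4/0.1) = 2. The simulation confirms this estimate is unbiased at every f.

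**The case against.** The strongest reply is that nothing in the documents shows an effect lasting 20 minutes. Manipulation is a single impulse and the head goes straight back to neutral. The protocol images blood flow first because change is more likely to be seen early, which fits a short-lived effect. With a half-life of 5 minutes or less the bias is about 3% or below. This stands as far as size is concerned. It does not show that carry-over is absent, because the documents give no duration, and the trial itself looks for effects that outlast the manoeuvre.

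A reader might infer more than the documents support in four ways:

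- *Carry-over runs only from manipulation into rotation.* Rotation is held for 1 minute and is followed directly by manipulation in the other order, so it could carry over too.
- *The contrast always shrinks.* It does when rotation has no effect, but it can widen when rotation has the larger effect in the same direction.
- *There is no washout at all.* About 20 minutes separate the manoeuvres. What is missing is any rest or neutral scan beyond that.
- *The whole trial is compromised.* Manipulation versus neutral is not affected by manipulation carry-over. It is affected by rotation carry-over, if there is any, and neutral always comes first, so it stays confounded with time.

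It is also fair to object that 20 participants cannot settle the matter. A carry-over test has very little power, and refusing to credit rotation with an effect unless the rotation-first group shows it would rest on about 10 people. Those objections stand and limit the fix.

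**Conclusion.** The concern holds in conditional form. The timing and the order of scans leave no neutral measurement between the manoeuvres, and neither model could reveal an effect of the first manoeuvre persisting into the second scan block. Under no rotation effect, equal orders and a remaining fraction f of the manipulation effect, the rotation-versus-manipulation contrast is understated by f/2 and rotation gains a false effect of f/2 of the manipulation effect: negligible at f = 0.06, 25% at f = 0.5, at most 50%. The documents support no particular f, and the direction of bias depends on the relative sizes of the two effects and on which of them persists. This is a limit on what the rotation contrasts can show, and by-order reporting makes it visible. It is not evidence that carry-over occurred.

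**What to change.** 1. Add period (first or second manoeuvre) and order to the VA flow analysis and to the ASL and BOLD analyses. The period term deals with drift between the two manoeuvres, which matters if the orders turn out unequal. It does not remove carry-over.
2. Report the number of participants in each order, and the rotation and manipulation changes from neutral separately by order.
3. Beside the pooled paired result, report as a sensitivity analysis the first-manoeuvre-only comparison of change from neutral (about 10 v 10) with its confidence interval.
4. Do not use a carry-over test to choose between analyses.
5. State in the conclusions that a null rotation-versus-manipulation result, or a rotation-versus-neutral effect, cannot exclude carry-over.
6. Reconcile the Test Protocols sentence about each manoeuvre beginning with neutral with the single neutral scan set and the 60-minute session, and say whether it means a starting position or a scan.

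The cost is analysis wording and a few extra outputs, with no new data. This matters because the protocol is written in the past tense and data collection appears complete. The downside is precision: the first-manoeuvre comparison has about twice the standard error of the paired one, so its interval will be wide. It supports interpretation and does not replace the paired test.
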